## 7. RESEARCH QUESTION AND OBJECTIVES

The primary objective of the study is:

- Description of direct costs related to warfarin/apixaban treatment during the first 6 months of the secondary stroke prevention in NVAF patients.

The secondary objectives of this study are:

- Comparison of direct costs related to warfarin/apixaban treatment during the first 6 months of the secondary stroke prevention in NVAF patients;
- Number of hospitalization days in the first 6 months of the treatment;
- Number of ischemic/hemorrhagic strokes in the first 6 months of the treatment;
- Number of ischemic events in the first 6 months of the treatment;
- Number of major/minor hemorrhagic events in the first 6 months of the treatment;
- Mortality rates in both cohorts;
- Number and costs of medical procedures directly related to the treatment in the first 6 months (visits, hospitalizations, labs, diagnostics, etc.);
- Overall safety (adverse events) of the treatment.

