## 8. RESEARCH METHODS

### 8.1. Study design

This is a double arm, non-interventional, single-center retrospective study according to Czech legal definitions (Law 378/2007 Sb.). For the description of the direct costs related to warfarin/apixaban treatment, retrospective data will be used for both, the warfarin treatment arm and the apixaban treatment arm.

The study follows two cohorts of NVAF patients, who used either warfarin or apixaban as a secondary stroke/TIA prevention.

The data to be collected retrospectively:

- Consecutive data of the 6 months after the first prescription of warfarin/apixaban (indicated as a secondary stroke/TIA prevention).

Considering the retrospective design of data collection, the non-interventional study will not impose any additional procedures, assessments or changes to the routine management of subjects. Data for the study will be obtained from clinical practice records and transcribed to an anonymous electronic case report form (e-CRF).

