## 8.2. Setting

In total, this non-interventional study follows the population of 240 patients with nonvalvular atrial fibrillation. From 240 NVAF patients, 120 patients are treated with warfarin and 120 patients are treated with apixaban.

The study will follow the period of 6 months after the prescription of warfarin or apixaban for the secondary stroke/TIA prevention.

The data will be collected retrospectively from clinical practice hospital records.

It's expected that the data will be collected within 3 months from the start of the study – the data collection will be closed as soon as there are 120 patients enrolled in each study arm. If there are not 120 patients enrolled in each study arm after 3 months of the data collection, the period can be prolonged up to 6 months from the start of the study.

Requirements for the center's eligibility are as followed: center able to genetically determine patients' higher sensitivity to warfarin; neurologists, who work in cerebrovascular center in a hospital; satisfactory experience in the care of patients with NVAF and treatment with warfarin and NOAC; sufficient number of patients with NVAF diagnosis fulfilling eligibility criteria.

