### 8.3. Variables

**Table 1:** Table of variables

Variable	Role	Data source(s)	Operational definition
Age, Sex, BMI, date of index event (stroke/TIA diagnosis), date of indication to warfarin/apixaban treatment (index date)	Demographic data	Medical records	Specified in e-CRF
CHA2-DS2-Vasc score, HAS-BLED score	Outcome	Medical records	Specified in e-CRF
Therapy after index event, prior to warfarin/apixaban treatment	Exposure	Medical records	Specified in e-CRF
Warfarin/apixaban therapy information (dosage; number of INR measurements in warfarin arm)	Exposure	Medical records	Specified in e-CRF
Number and type of resource use during the first 6 months of warfarin/apixaban treatment (outpatient visits, diagnostic procedures, labs, medication, hospital admissions)	Outcome	Medical records	Specified in e-CRF
Amount, type, severity and cost of ischemic events	Outcome	Medical records	Specified in e-CRF

Amount, type, severity and cost of major/minor hemorrhagic events	Outcome	Medical records	Specified in e-CRF
Adverse events	Outcome	Medical records	Specified in e-CRF

*Index date = The index date will be the first date of OAC prescription indicated for secondary stroke/TIA prevention.*

*Index event = The index event will be the first stroke/TIA event based on which the OAC treatment will be initiated.*

*Index event date = The index event date will be the date of first stroke/TIA event based on which the OAC treatment will be initiated*

*Therapy after index event, prior to warfarin/apixaban treatment (Aspirin, clopidigrel, Trombolytics (rhu-tPA - alteplase, urokinase), Anticoagulants (heparin, heparinoids), other)*

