#### **8.5. Study size**

The study will be descriptive in nature. No sample size was statistically determined. Based on experience of experts on anticoagulant treatment the data from 120 patients per study arm can be collected.

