### **8.7. Data analysis**

The statistical analyses will be descriptive and exploratory. Given the nature of the study, which is exploratory, it is not designed to confirm or reject predetermined hypotheses.

Categorical outcomes will be summarized by the number and percentage in each category. Continuous outcomes will be summarized by mean, standard deviation, median, minimum and maximum values.

All analyses will be based on the full analysis set, comprising all subjects enrolled into the study.

The paired tests will be applied in the detailed analyses. Relevant endpoints will be compared using the differences in mean / median or proportion. Statistical significance will be assessed at a significance level of 0.05. All statistical analyses will be conducted using STATA version 13.1.

**Table 2:** Table of descriptive analyses

Variable	Categorical outcome	Continuous outcome
Age		X
Sex	X	
Body height, weight, BMI		X
Period between stroke/TIA and start of secondary stroke prevention (duration in days)		X
Period between stroke/TIA and start of secondary stroke prevention (medication)	X	
CHA2-DS2-VASc Score		X
Stratification: (0, 1, 2-9)	X	
HAS-BLED Score		X
Stratification: (0-2, 3-9)	X	
Warfarin/apixaban dosage		X
INR measurements	X	
Number and type of outpatient visits, diagnostic procedures, labs, hospital admissions	X	
Cost of outpatient visits, diagnostic procedures, labs, medication, hospital admissions		X
Amount, type and severity of ischemic events	X	
Cost of ischemic events		X
Amount, type, severity of major/minor hemorrhagic events	X	

Cost of major/minor hemorrhagic events		X
Adverse events	X	

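### Section 8.7 compares two non-randomised cohorts, selected by different criteria, through crude differences tested at 0.05, so any imbalance in measured case mix would bias the secondary comparisons

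*Combined protocol and SAP*

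**What the plan says.** The primary objective in section 7 is descriptive. The first secondary objective is comparative: "Comparison of direct costs related to warfarin/apixaban treatment during the first 6 months of the secondary stroke prevention in NVAF patients". The closing paragraph of section 6 also gives comparison of resource use as the reason for the study.

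Section 8.1 sets the design: "This is a double arm, non-interventional, single-center retrospective study according to Czech legal definitions". Section 8.2 fixes the arm sizes: "From 240 NVAF patients, 120 patients are treated with warfarin and 120 patients are treated with apixaban". Section 8.5 adds "No sample size was statistically determined". In section 8.2.1, inclusion criterion 4 requires genetically determined warfarin sensitivity in the apixaban arm and sets no genotype requirement for warfarin.

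Section 8.7 labels the analyses descriptive and exploratory, calls for paired tests in the detailed analyses, and then says "Relevant endpoints will be compared using the differences in mean / median or proportion", judged at 0.05. Table 1 in section 8.3 collects demographics (the row opening "Age, Sex, BMI, date of index event (stroke/TIA diagnosis"), "CHA2-DS2-Vasc score, HAS-BLED score" and therapy between the index event and the start of oral anticoagulation. Table 2 summarises these variables. The comparison rule does not use them.

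**The concern.** In a non-randomised comparison, a crude difference mixes any treatment effect with whatever else differs between the arms. Age, vascular risk and bleeding risk plausibly drive admissions, events and cost. If the arms differ on them, the crude difference is shifted by an amount that the standard error does not reflect, and the 0.05 test no longer has a 5% error rate.

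The exposed results are the secondary comparisons of cost, hospital days and events. Section 6 calls real-world data on resource use and costs essential to establishing the value of new therapies, so readers are likely to use these comparisons. The variables needed to reduce the bias are already on the collection list.

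**Working it through.** **Is there any adjustment elsewhere?** I looked for one in three places.

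- The stratification rows in Table 2 for the two scores define categories for a descriptive table. They are not a stratified estimate.
- The paired-tests sentence in section 8.7 could imply matching, but no pair, matching variable or matching procedure is defined for two separate cohorts of 120. It adjusts for nothing.
- Section 8.9 says both cohorts meet the same inclusion criteria, which criterion 4 contradicts. It names random distribution of patients between treatments as the main limitation and does not mention confounding.

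So the only defined between-arm method is the crude difference.

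**How large could the effect be?** The plan has no power, effect-size or SD figure to reproduce. What follows is an illustration.

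Inputs from the plan: n = 120 per arm (section 8.2) and alpha = 0.05 (section 8.7). Sidedness is not stated, so two-sided is assumed.

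Inputs assumed: no drug effect, one baseline covariate with between-arm imbalance d (in SD units), within-arm correlation r between that covariate and the outcome, and a normal outcome with SD 1 within arm. The documents give neither d nor r.

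Formulas:

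- SE of the crude difference = sqrt(2/120) = 0.129 SD. The significance threshold is 1.96 × 0.129 = 0.253 SD.
- Bias = d × r.
- False-positive rate = P(Z > 1.96 − bias/SE) + P(Z < −1.96 − bias/SE).

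| d | r | bias (SD) | bias/SE | false-positive rate |
|---|---|---|---|---|
| 0 | any | 0 | 0 | 5.0% |
| 0.1 | 0.2 | 0.02 | 0.15 | 5.3% |
| 0.2 | 0.3 | 0.06 | 0.46 | 7.5% |
| 0.3 | 0.3 | 0.09 | 0.70 | 10.7% |
| 0.3 | 0.4 | 0.12 | 0.93 | 15.3% |
| 0.3 | 0.5 | 0.15 | 1.16 | 21.3% |
| 0.5 | 0.5 | 0.25 | 1.94 | 49.1% |

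**Does adjustment help under the same assumptions?** A simulation of 4,000 replicates compared a t-test with a linear model that included the covariate.

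- d = 0.3, r = 0.3: false positives fell from 10.5% to 5.1%, and the SD of the estimate went from 0.129 to 0.125.
- d = 0.5, r = 0.5: false positives fell from 50.1% to 5.1%, and the SD of the estimate went from 0.130 to 0.116.

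The return to about 5% is built into this set-up, which has a single confounder, fully measured and correctly modelled. It shows the mechanism. It does not show that adjustment would restore the nominal rate in this study. Costs are also likely to be skewed, which the normal model ignores.

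**The case against.** **The comparison is secondary and exploratory.** The title and primary objective are descriptive, section 8.7 disclaims hypothesis confirmation, and the study size is a feasibility count. This stands as far as severity goes: arm-level summaries meet the primary objective without adjustment. It does not remove the point, because a between-arm comparison is a listed objective and is tested at 0.05. An exploratory estimate can be confounded too.

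**Genotype may act almost like random allocation.** Every apixaban patient must carry the sensitivity genotype, and nothing in the documents links genotype to age, BMI or the risk scores. To the extent that genotype alone decided treatment, expected imbalance on those variables is near zero. But the documents do not say who was tested, whether all sensitive patients received apixaban, or whether warfarin patients were tested at all.

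Calendar time could also differ. Suppose everyone were tested and treated by genotype, and the roughly 30% sensitivity that section 6 quotes for healthy Czech subjects applied. Then 120 apixaban patients would need about 120/0.3 = 400 candidates, and 120 warfarin patients about 120/0.7 = 171. The arms could then cover different periods.

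**Stronger readings.** A reader might infer that the plan attributes any difference to the drug, or that the arms are known to be imbalanced. Neither is supported. Section 8.7 reports differences without a causal claim, and no baseline data are given.

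**Conclusion.** The point holds as a conditional risk and should be fixed. As written, the plan compares non-randomised, differently selected cohorts without adjustment, so any imbalance in measured case mix would bias the secondary comparisons. The primary description of costs is unaffected.

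The size is unknown. The span from 5% to about 49% rests on assumed imbalance and correlation, a two-sided test, one covariate and a normal outcome. A reader might take 49% as the expected error rate, but it is the upper corner of an assumed grid, and mild imbalance barely moves the rate (5.3% at d = 0.1, r = 0.2).

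Nor would adjustment make the comparison causal. Genotype governs entry to one arm and is not a Table 1 variable, and severity of the index event is not explicitly recorded there.

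**What to change.** In section 8.7, replace the paired-tests sentence and the comparison sentence with one method, fixed before database lock. For example:

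> Between-arm differences in mean total direct cost, mean hospitalisation days and event proportions will be estimated by overlap weighting. The propensity score will include age, sex, BMI, CHA2DS2-VASc and HAS-BLED at the index date, therapy between the index event and anticoagulant start, and calendar year of the index date. Confidence intervals will be obtained by bootstrap, with the propensity model refitted in each resample. Standardised mean differences before and after weighting will be tabulated, and the crude difference shown alongside.

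One weighting model serves all three outcome types and avoids fitting a many-covariate outcome model to what may be few events in six months.

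In Table 1, define the two scores as values at the index date with a baseline role. They are now listed as outcomes with no time point.

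In section 8.9, state that the arms do not meet the same inclusion criteria, that adjusted results are associations, and that confounding by genotype-based selection and unrecorded index-event severity remains.

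The cost is wording and a modest amount of code. No new variables are needed if the e-CRF, which is not among the documents, records the scores at the index date. The downsides are small: one model choice has to be committed to in advance, weighting may cost some precision, and the estimate then describes patients whose measured characteristics overlap between the arms.

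### Section 8.7 lets costs be compared by mean or median at the 0.05 level without saying which, and plans no confidence interval

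*Combined protocol and SAP*

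**What the plan says.** All of the analysis text is in Section 8.7.

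- **Comparison:** relevant endpoints are to be "compared using the differences in mean / median or proportion". No rule assigns mean or median to an endpoint.
- **Decision rule:** "Statistical significance will be assessed at a significance level of 0.05".
- **Test family:** "The paired tests will be applied in the detailed analyses". No test is named for any endpoint, and no matching of the two cohorts is described.
- **Description:** "Continuous outcomes will be summarized by mean, standard deviation, median, minimum and maximum values". Quartiles and confidence intervals are not listed, and no section mentions an interval, a bootstrap, a transformation or any handling of skewness or zeros.
- **Status:** the study is labelled exploratory, and "it is not designed to confirm or reject predetermined hypotheses".

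In Section 7 the primary objective is to describe direct costs. Comparing them is the first secondary objective, and another is "Number of hospitalization days in the first 6 months of the treatment". Table 2 marks every cost row as continuous. It has no row for hospital days; admissions appear there as categorical. Section 8.2 gives the size: "120 patients are treated with warfarin and 120 patients are treated with apixaban".

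**The concern.** A cost total usually has two parts: drug, visit and monitoring costs that every patient incurs, and large costs for the few who have a stroke, a bleed or an admission. Section 6 expects apixaban to bring fewer visits, less monitoring and fewer complications. The complication part sits in the upper tail, which a median largely ignores. Multiplying the arithmetic mean by the number of patients gives the cost of the cohort; multiplying the median does not.

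If routine cost is higher in one arm and costly events are more frequent in the other, the two measures answer different questions and can point in different directions. With the measure left open, the choice can be made after the data are seen, and the significance statement on cost can depend on it. Without an interval, the report need not show how little 120 charts per arm may settle about a skewed mean.

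**Working it through.** The plan states no cost, SD, event rate or power, so it has no figure to reproduce. Only n = 120 per arm and α = 0.05 come from the documents, plus two risk reductions cited in Section 6 and used in step 2. Every other input is an assumption in arbitrary units. The plan names no rank test; Mann-Whitney is used here as the usual companion to a median comparison.

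**1. A fixed example.** Warfarin: 100 for everyone, plus 1,000 in 18 of 120. Apixaban: 130 for everyone, plus 1,000 in 6 of 120.

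- Means: 100 + 1,000 × 18/120 = 250, and 130 + 1,000 × 6/120 = 180. Difference −70.
- SDs are 358.6 and 218.9, so SE = √(358.6²/120 + 218.9²/120) = 38.3. The 95% CI is −70 ± 1.96 × 38.3, or −145 to +5 (Welch p = 0.069).
- Medians: 100 and 130. Difference +30 (Mann-Whitney p < 0.001).

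The same data give a lower mean for apixaban, not significant, and a higher median, highly significant on the rank test.

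**2. Simulation.** Routine cost is lognormal with log-SD 0.4, median 100 for warfarin and 130 or 200 for apixaban. Event cost is lognormal with median 1,000 and log-SD 0.8. Warfarin event risk is 12%. True mean = routine median × exp(0.08) + risk × 1,000 × exp(0.32). For warfarin this is 108.3 + 0.12 × 1,377.1 = 273.6; the true median is 107. Each row uses 10,000 simulated studies of 120 per arm.

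| Apixaban routine median | Apixaban event risk | True mean | True median | Opposite signs | Rank test p < 0.05 | Welch p < 0.05 |
|---|---|---|---|---|---|---|
| 130 | 6% (halved) | 223.5 | 134 | 76% | 89% | 9% |
| 130 | 8.28% (31% lower) | 254.9 | 136 | 60% | 92% | 5% |
| 130 | 9.48% (21% lower) | 271.4 | 137 | 50% | 94% | 4% |
| 130 | 12% (equal) | 306.1 | 139 | 34% | 96% | 7% |
| 200 | 6% (halved) | 299.3 | 206 | 35% | 100% | 9% |

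The 21% and 31% reductions are those that Section 6 cites for stroke or systemic embolism and for major bleeding with apixaban against warfarin. Applying either to all costly events is an assumption. In the first three rows the true mean is lower and the true median higher for apixaban. In the last two, both are higher for apixaban, and the opposite signs are sampling error in the mean. A reader would recognise that only from an interval.

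**3. Hospital days.** Assume 20% v 10% of patients are admitted, for 8 days on average, and the index stay is not counted. Means are 0.20 × 8 = 1.6 and 0.10 × 8 = 0.8. An arm's median is 0 whenever fewer than 60 of 120 are admitted; with Binomial(120, 0.20) and Binomial(120, 0.10), the probability that both medians are 0 exceeds 0.999. At 40% admitted, the probability for that arm is still 0.98. Costs of events behave the same way when patients without an event count as zero.

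**4. Precision.** The 95% half-width as a fraction of the mean, with equal means and CVs:

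- One arm: 1.96 × CV/√120 = 0.18 at CV 1 and 0.36 at CV 2.
- Difference: 1.96 × CV × √(2/120) = 0.25 at CV 1 and 0.51 at CV 2.

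**The case against.** The strongest reply is that the study is descriptive and exploratory, and that means, SDs and medians will all be tabulated. The arithmetic mean is therefore reported whatever is tested, and a reader can derive an approximate interval from the mean, the SD and the number of patients. The slash could also mean that both differences are reported, which would expose a conflict. All of this stands, and it lowers the severity. It does not close the point: a 0.05 verdict is still planned on an unnamed measure, and nothing commits the report to an interval.

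It can also be said that the size of the problem rests on chosen inputs. That is correct. A reader might take the 76% as a property of this plan; the documents contain no costs or event rates to support that, and other plausible inputs bring it down to about 34%.

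Three further inferences go beyond the text:

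- That the primary objective is undermined. It is descriptive, and the mean and SD are already planned for it.
- That total direct cost is mostly zeros. Patients on treatment have drug and visit costs; disagreement in the total comes from skewness.
- That hospital days could reverse direction in the same way. When most patients have none, the median hides a difference. If the index stay counts, days may not be mostly zero, and the documents do not say whether it does.

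**Conclusion.** The point holds and should be fixed, but it is not critical to the study. The plan allows two measures for the cost comparison that can disagree in sign and significance, does not choose between them, and plans no interval. In the scenarios shown, opposite signs occurred in about 34% to 76% of studies. These figures show that disagreement is a practical possibility at 120 per arm; they do not predict what this study will find. They rest on assumed right-skew, routine costs and event risks.

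The effect falls mainly on the secondary cost comparison, and on event costs and hospital days where zeros predominate. For the primary objective, the only gap is an interval around each arm's mean.

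**What to change.** Keep the comparison of proportions for binary outcomes and add to Section 8.7:

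> Costs, hospitalisation days and resource counts will be compared between the two independent cohorts by the difference in arithmetic means per enrolled patient (patients without an event or admission counted as zero) with a bootstrap 95% CI. Each arm's mean direct cost is reported with its 95% CI. Medians and quartiles are descriptive only.

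For these comparisons, replace the paired tests with independent-group methods, since no pairing is described. It would also help to state whether days of the index stay count as hospital days.

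The cost is a few lines of text and a bootstrap run. No new data are needed. The small downside is that the intervals will be wide, about ±25% to ±51% of the mean for the difference at an assumed CV of 1 to 2. That imprecision exists already; the change makes it visible.

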## 8.8. Quality control

Data entry into eCRF and Electronic Data Record will be accomplished by qualified subjects only. Entered data will be reviewed by CRO for consistency and logic via implemented quality checks and by manual reviews, as well.

